Systemic lupus erythematosus (SLE) is a prototypic autoimmune disease whose heterogeneity has confounded scientists, clinicians, and patients for decades. Current therapeutic efforts are directed at the inflammation that causes organ damage, yet patients often remain disabled by fatigue, myalgia, mood disturbance, and cognitive dysfunction. These symptoms are persistent and often resistant to immunosuppression.

At Duke, we have developed a new conceptual model that characterizes SLE activity into two dimensions:

- Type 1: Classically considered SLE activity and recorded in physician-reported measures of SLE activity. Includes synovitis, rashes, serositis, nephritis, CNS lupus, and other objective signs.
- Type 2: Symptoms of fatigue, myalgia, mood disturbance, and cognitive dysfunction; typically not included in physician-reported measures of SLE, but are frequently reported by patients. Physicians

may ascribe these symptoms to depression or fibromyalgia, while patients identify them as SLE-related.

We hypothesize that Type 1 and 2 SLE activity varies in intensity over time, including some periods of minimal activity (neither Type 1 or 2) and mixed activity (both Type 1 and 2).

Patient-reported measures have had limited acceptance in the study of SLE, possibly due to the incongruence between Type 1 physician-reported activity and Type 2 patient-reported symptoms. According to over 1000 patients with SLE, a patient-defined-flare includes extreme fatigue (87% of the flares), aching joints (80%), muscle weakness or pain (74%), and forgetfulness (61%). Of these symptoms, only aching joints would be counted as active lupus by a rheumatologist; the remaining symptoms are likely Type 2 activity of SLE. While the authors of this study suggested that we need to re-educate our patients about lupus flares, we suggest we change how we think about SLE.

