We are currently piloting two patient-reported outcomes (PRO) measures for Type 1 and 2 SLE: The Fibromyalgia Severity Score (FSS) allows patients to indicate areas of pain, extent of fatigue, waking unrefreshed, and cognitive symptoms. The FSS was designed to diagnose fibromyalgia, but we have found this scale clinically useful to efficiently measure the current extent of Type 2 SLE symptoms. The Systemic Lupus Activity Questionnaire (SLAQ) is a 24-symptom patient-reported measure of SLE activity. It partially correlates with the physician-reported Systemic Lupus Activity Measure. We have found the SLAQ clinically useful in highlighting important symptoms for patients, but the current scoring system combines Type 1 and 2 SLE activity, resulting in an assessment that is not clinically actionable.

The proposed research will build a brief preliminary PRO measure that combines features of the FSS and the SLAQ to indicate the current degree of Type 1 and Type 2 SLE activity, allowing for rapid assessment and appropriate treatment in practice.

The overall objective of this study is to develop a composite measure based on our conceptual model of Type 1 and 2 SLE to distinguish between these two symptom complexes, and then conduct a pilot implementation study of the measure within Duke Rheumatology. The central hypothesis is that Type 1 and 2 SLE are clinically distinct components of SLE that, once distinguished, will lead to improvements in the clinical management of SLE.

Methods:

Aim 1: Ensure the Type 1 and 2 SLE model matches the patient experience with lupus.

We will conduct a qualitative, descriptive study. For objective #1, we will conduct in-depth interviews. For objective #2, we will conduct cognitive interviews. In-depth interviews will be completed prior to cognitive interviews. Information learned in the in-depth interviews to develop patient-reported measures will be reviewed in the cognitive interviews.

In-depth interviews: During the in-depth interviews, participants will be asked to share their perspective on the experience with Type 1 and 2 SLE symptoms, treatments, and how their experience with lupus fits with the Type 1 and 2 SLE model. (See attachment for the question guide).

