In-depth interviews: We will conduct 12 to 15 interviews with individuals who experience higher Type 2 symptoms and 12-15 interviews with individuals who experience lower Type 2 symptoms. We chose these samples sizes because thematic saturation is typically reached around 12 interviews (Guest 2006). The interviewers will assess based on informational redundancy whether 3 additional interviews are needed.

Cognitive interviews: We will conduct at least two rounds of 10 cognitive interviews. Each round will include five participants who experience higher Type 2 symptoms and five participants who experience lower Type 2 symptoms. If further changes are necessary to the measures reviewed during the initial two rounds cognitive interviews, an additional six interviews will be conducted.

Participant selection and recruitment: We will purposefully select participants (Patton 2005) to identify the range of experiences. We will enroll a diverse study population with respect to 1) race (i.e., white and African American individuals) and 2) age (i.e., a range of ages, with an emphasis on recruiting young women). We will also stratified based on individuals' experience with higher versus lower Type 2 symptoms. These classifications will be based patient- and physician-reported measures from the prior visit to the Duke Lupus Clinic. High Type 1 symptoms will be defined as a SLEDAI score ≥ 6 (Gladman 2002). High Type 2 symptoms will be defined as a fibromyalgia severity score (widespread pain index + symptom severity index) ≥ 12 (Wolfe 2011).

Lupus Clinic is held each Wednesday in Duke South Clinic 1J. Prior to each weekly clinic, the patient list will be reviewed to identify potentially eligible patients. Eligibility will be determined based on information obtained from the medical record, as well as through a discussion with the individual's treating rheumatologist in the Duke Lupus Clinic. Prospective participants will be approached about the study during routine clinic visits at the Duke Lupus Clinic. The study will be introduced by the individual's Duke Rheumatologist.

Reimbursement: Participants will receive \$25 to reimburse them for their time participating in each interview.

Data Analysis: We will use descriptive statistics to summarize the demographic data and applied thematic analysis to analyze the qualitative data from the in-depth interviews and cognitive interviews.

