- **Physician-reported measures:** Systemic Lupus Erythematosus Disease Activity Index (SLEDAI), Physician's Global Assessment, LFA-REAL
- **Routine Lupus Labs:** CBC with differential, creatinine, C3 and C4, anti-dsDNA antibody, C-reactive protein, sedimentation rate, complete urinalysis, and urine protein:creatinine

Data Analysis: Robust cluster analysis. [name] will expand on our preliminary cluster analysis using latent profile analysis to include detailed patient-, physician- and laboratory measures. **Power Calculation:** In order to identify 4 clusters using 8 predictive variables, a minimum sample size of 320 patients is needed. If the cluster analysis identifies 7 distinct clusters, there will be sufficient power to include 5 predictive variables in the model with 350 patients. Differences in phenotypes across clusters, including patients' demographic, SLE history, patient- and physician-reported measures, and laboratory tests will be estimated by ANOVA and Chi-squared test.

Using our new knowledge about the quantitative differences in SLAQ responses by cluster, the qualitative information about symptoms from patient interviews, and clinical expertise, we will revise the SLAQ and create a new scoring system with individual Type 1 and 2 SLE scores. This new scoring system will be tested using 800 patient visits to determine if the new Type 1 and 2 SLE scores correspond to cluster assignment. Using logistic regression models, [name] will compare three commonly used physician-reported SLE measures, the SELENA-SLEDAI, physician's global assessment, and LFA-REAL™ to determine if model fit improves with physician-reported measures. Goodness of fit will be assessed by the Hosmer-Lemeshow chi-square test, and model discrimination will be assessed using C statistics to estimate the area under the receiver operating characteristic curve. To account for patients potentially contributing more than one visit to this analysis, generalized estimating equations (GEE) will be used.

Inclusion: Patients who are enrolled in the Duke Lupus Registry and gave informed consent through the Duke Lupus Registry (DLR) (IRB Pro00008875) and Sub-studies of the DLR (IRB Pro00094645).

Compensation: Data collected from patients enrolled in the Duke Lupus Registry will be retrospectively analyzed. No compensation will be provided as part of this analysis.

Aim 3. Conduct a pilot implementation study of the Type 1 and 2 SLE model into clinical care.

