To impact patients, the Type 1 and 2 SLE model needs to be translated into an actionable tool. The overall goal of Aim 3 is to develop and test a set of electronic medical record (EMR)-based tools that enable rheumatologists to assess, discuss, and treat Type 1 and 2 SLE.

Tool Development. Over the past year, the physicians in the Duke Lupus Clinic have organically developed approaches to assessing and discussing Type 1 and 2 SLE with their patients. [name] will work with the providers in the Lupus Clinic to iteratively create SLE@Duke, a set of EMR-based tools to implement the Type 1 and 2 SLE model into clinical practice. Components will include a templated lupus note, dotphrases to assess and explain Type 1 and 2 SLE, the PRO survey, patient handouts, and suggested treatment plans. [name] will assess provider satisfaction quarterly at the Lupus Clinic Meeting as SLE@Duke tools are tested in clinic, making iterative changes based on their feedback.

Pilot Testing. This aim will pilot the SLE@Duke program with the Duke Rheumatologists outside of the Duke Lupus Clinic, where an estimated one-third of Duke Rheumatology's SLE patients are seen by 11 rheumatologists and 4 nurse practitioners. Non-Lupus Clinic providers and patients will complete surveys to assess satisfaction with visits and the treatment of SLE.

Interventions. SLE@Duke. The components of SLE@Duke will be made available in Epic for providers to assess and discuss patients' Type 1 and 2 SLE activity at each clinic visit. Physician & Clinic Training will include Rheumatology Division Grand Rounds and in-person Academic Detailing sessions in each of the clinics. Accompanied by a Duke Lupus Clinic provider, [name] will make frequent visits to the rheumatology clinics at 1J, Brier Creek, and South Durham to introduce the surveys, educate the nursing staff and providers on Type 1 and 2 SLE, and troubleshoot any issues that arise. The goal of these visits will be to introduce SLE@Duke, as well as solicit feedback on how to improve the tool.

Outcomes & Evaluation. We will use the RE-AIM framework to guide our collection of comprehensive information about the reach, effectiveness, adoption, implementation, and maintenance of SLE@Duke (Table 1)²⁵.

Table 1: RE-AIM Framework for Implementation Assessment

Provider-Level Outcomes	Patient-Level Outcomes
REACH: participant characteristics; differences between participants & non-participants	

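### The patient-reported Type 1 score is validated only indirectly, through clusters and model fit; a direct comparison with SLEDAI, LFA-REAL and renal results should be added

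*Combined protocol and SAP*

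**What the plan says.** All references are to the combined protocol and SAP.

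- **What Type 1 is (Background & Significance).** Type 1 is the activity that physician-reported measures record. The text adds: "Includes synovitis, rashes, serositis, nephritis, CNS lupus, and other objective signs".
- **What the measure is for (Background & Significance).** The brief patient-reported measure is meant "to indicate the current degree of Type 1 and Type 2 SLE activity, allowing for rapid assessment and appropriate treatment in practice". The same section says that the SLAQ, on which it builds, agrees only in part with a physician-reported measure.
- **How the clusters are formed (Aim 2, Data Analysis).** The preliminary cluster analysis will be extended by "latent profile analysis to include detailed patient-, physician- and laboratory measures". Physician measures and laboratory tests are also compared across clusters by ANOVA and chi-squared test.
- **How the score is built and tested (same section).** The SLAQ is revised using differences in its responses between clusters, the interviews and clinical expertise. The resulting scores are "tested using 800 patient visits to determine if the new Type 1 and 2 SLE scores correspond to cluster assignment".
- **How physician measures enter the test (same section).** SELENA-SLEDAI, physician's global assessment and LFA-REAL are compared in logistic models "to determine if model fit improves with physician-reported measures". The statistics named are Hosmer-Lemeshow and the C statistic, with GEE for repeat visits.
- **A physician-based cut-off (Aim 1, Participant selection and recruitment).** "High Type 1 symptoms will be defined as a SLEDAI score ≥ 6". It is used there to classify interview participants and does not reappear in Aim 2.
- **Use (Aim 3, Tool Development).** The components of SLE@Duke include "the PRO survey, patient handouts, and suggested treatment plans".

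**The concern.** A score that claims to indicate Type 1 activity should be compared with Type 1 activity as the plan defines it. That definition rests on objective findings, and a patient may have some of these without noticing them. The stated target for the score is instead cluster assignment. The clusters draw partly on patient answers, and differences in SLAQ responses between clusters are used to build the score, so some agreement is built in. The plan cites 800 registry visits for both development and testing and states no separation between them.

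If visits with active but unfelt disease score low, Aim 2 could report good discrimination without identifying them. Aim 3 then makes the survey available in Epic, and Table 1 counts treatment according to the extent of Type 1 and 2 SLE as an adoption outcome. None of the Table 1 outcomes checks the accuracy of the score, so Aim 2 is the place to look.

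**Working it through.** **1. The plan's own figures.** The Power Calculation asks for 320 patients (4 clusters, 8 variables) and 350 patients (7 clusters, 5 variables). Both fit 10 × clusters × variables: 10 × 4 × 8 = 320 and 10 × 7 × 5 = 350. The plan does not name this rule; it is inferred from the fit. The figures matter here only because they show that 5 to 8 variables are foreseen, shared among patient, physician and laboratory measures. The split is not given.

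**2. What each planned analysis compares.**

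| Planned analysis (Aim 2) | Compared with what | What it leaves open |
|---|---|---|
| Scores vs. cluster assignment | Clusters of mixed origin, weights unstated | Whether a visit with high SLEDAI has a high Type 1 score |
| Model fit with physician measures | The logistic outcome is not named; from context, cluster | Which visits the score misses; fit may improve simply because the same measures helped form the clusters |
| ANOVA and chi-squared across clusters | Clusters, not the score | How the score behaves within a cluster |

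No row sets the Type 1 score directly against SLEDAI, LFA-REAL, urinalysis or urine protein:creatinine.

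**3. Does the planned test react to unfelt disease?** This was examined by simulation. Every effect size is an assumption, so only the direction counts.

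- Set-up: 800 independent visits, 12 runs per setting, Type 1 active in 35% and Type 2 in 45%, four latent profiles.
- Clusters were formed either from eight variables (four patient, four physician or laboratory) or from the four patient variables alone.
- A cluster counted as high Type 1 if its mean SLEDAI was clearly above the overall mean. Membership was modelled on the two patient scores, then with SLEDAI added.
- The score cut-off was the 80th percentile among visits without Type 1 activity.

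| Clusters formed from | Unfelt share of active Type 1 | C, scores only | C, SLEDAI added | Likelihood-ratio statistic | Unfelt visits in a high-Type-1 cluster |
|---|---|---|---|---|---|
| Patient, physician, laboratory | 0% | 0.93 | 0.99 | 268 | – |
| | 10% | 0.89 | 0.97 | 316 | 87% |
| | 20% | 0.84 | 0.96 | 359 | 92% |
| | 30% | 0.79 | 0.96 | 403 | 92% |
| Patient only | 0% | 0.98 | 0.98 | 8.1 | – |
| | 10% | 0.98 | 0.98 | 8.1 | 4% |
| | 20% | 0.99 | 0.99 | 6.8 | 3% |
| | 30% | 0.99 | 0.99 | 4.1 | 3% |

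- With physician and laboratory measures in the clusters, C falls from 0.93 to 0.79. The planned test does react.
- The reaction is not specific. Adding SLEDAI improves fit strongly (268, against a 5% critical value of 3.84) even when no disease is unfelt.
- With patient-driven clusters, C does not fall and the likelihood-ratio statistic shrinks as the unfelt share grows. The problem is hidden.
- The plan's clusters are of the first kind in principle. Because the weights are unstated, how close they come to the second is unknown.

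**4. What a direct check shows in the same simulation.** Sensitivity was 0.88 for felt disease and 0.18 to 0.19 for unfelt disease. The second figure is close to the false-positive rate of 1 − 0.80 = 0.20, as it must be when the score is assumed to carry no information on unfelt disease; it is an input rather than a finding. Pooled sensitivity at a 10% unfelt share is 0.90 × 0.88 + 0.10 × 0.19 = 0.81, and at 30% it is 0.70 × 0.88 + 0.30 × 0.19 = 0.67. Even a direct pooled sensitivity can look acceptable at a small unfelt share, so the missed visits also need to be tabulated by cause.

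**The case against.** The strongest reply is that the plan already involves physician and laboratory data in three ways: in forming the clusters, in comparing phenotypes across them, and in the model-fit comparison. Enough unfelt disease in a low-symptom cluster would raise that cluster's SLEDAI or urine values, and in the simulation closest to the plan the C statistic did fall. This stands. A reader might infer that the Type 1 score is never set against physician-measured activity, or that the planned test cannot reveal unfelt disease; Aim 2, Data Analysis supports neither. What remains is that these checks are indirect and do not locate the missed visits.

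Second, SLEDAI ≥ 6 is an Aim 1 selection rule. A reader might take it as the plan's reference standard for Aim 2, but the document does not make it one. It is a convenient cut-off already in the plan, and using it does not justify replacing the cluster analysis.

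Third, the measure is called preliminary, providers assess activity themselves, and Aim 3 details await an addendum. A reader might infer that a low score would steer treatment alone; nothing in the document says so. This limits the urgency. It does not remove the gap, because the stated purpose is still to indicate the current degree of Type 1 activity.

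**Conclusion.** The point holds in a limited form. The Type 1 score is validated only indirectly, and no direct agreement with the physician and renal measures that represent Type 1 is planned. The existing checks may signal a shortfall, but a pooled C statistic can hide it, and improved fit neither identifies its cause nor names the visits.

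No size can be stated for this study. The share of active Type 1 visits without reportable symptoms is not in the documents, and any sensitivity figure would follow from whatever share is assumed. The simulation rests on assumed effects and independent visits, and shows direction only. The conclusion itself depends on two readings of the text: that Type 1 means objective, physician-recorded activity, and that the logistic outcome is cluster assignment, which the wording implies but does not state. The change is worth making before the score is used in Aim 3, but it does not invalidate the planned analysis.

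**What to change.** Keep the cluster analysis and add the following to Aim 2, Data Analysis, from data already collected at each visit:

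1. The association of the Type 1 score with SLEDAI and with LFA-REAL at the same visit.
2. Sensitivity and specificity of the Type 1 score for SLEDAI ≥ 6, acknowledging that this cut-off comes from Aim 1 selection, with GEE or patient-clustered intervals. Fix the cut-off of the Type 1 score before this analysis, and say whether SLEDAI or SELENA-SLEDAI is used, since the Aim 2 text names both.
3. A table of SLEDAI ≥ 6 visits with a low Type 1 score by the SLEDAI items responsible, with renal and laboratory items shown separately. This assumes that SLEDAI is stored by item; if it is not, the same-visit urinalysis, urine protein:creatinine, complement and anti-dsDNA results can serve.
4. A sentence that any statement that the score indicates Type 1 activity will rest on both the cluster analysis and these results. If the missed visits are mainly laboratory or renal, describe the score as *patient-reported Type 1 symptoms*, also in SLE@Duke.
5. The outcome of the logistic models, and the variables that enter the latent profile analysis.

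The cost is a few lines of text and one more table, with no new data collection. The score's reported performance may look less favourable.

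### Aim 2 tests three physician measures against clusters that physician measures help define, so a gain is not independent added value, and their ranking is unfair unless all three are treated alike

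*Combined protocol and SAP*

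**What the plan says.** All of this is in the combined protocol and SAP, Aim 2.

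- **Cluster inputs.** Data Analysis expands the preliminary cluster analysis "using latent profile analysis to include detailed patient-, physician- and laboratory measures". The individual inputs are not named.
- **Physician measures available.** Data Collection lists three: SLEDAI, physician's global assessment and LFA-REAL.
- **Size of the cluster model.** The Power Calculation gives 320 patients to "identify 4 clusters using 8 predictive variables". For 7 clusters it says "there will be sufficient power to include 5 predictive variables in the model with 350 patients".
- **Building the scores.** The SLAQ is revised "Using our new knowledge about the quantitative differences in SLAQ responses by cluster", together with interview findings and clinical expertise. The result is tested on 800 visits "to determine if the new Type 1 and 2 SLE scores correspond to cluster assignment".
- **Testing the physician measures.** Logistic models compare SELENA-SLEDAI, physician's global assessment and LFA-REAL "to determine if model fit improves with physician-reported measures". The outcome of these models is not restated.
- **Criteria.** "Goodness of fit will be assessed by the Hosmer-Lemeshow chi-square test", and C statistics are used for discrimination. GEE is used for repeated visits.

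**The concern.** A classification built partly from a measure will be predicted partly by that measure. If SLEDAI helps to decide which cluster a visit falls in, adding SLEDAI to a model of cluster membership should raise C even where it tells us nothing beyond its own role in drawing the boundaries. The plan neither keeps the tested measures out of the clustering nor limits how a gain may be read.

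The comparison among the three is more exposed. If one is a cluster input and the others are not, that one has an advantage unrelated to its merit.

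This step is where the plan would learn what a patient-reported form loses without a physician measure, and how the three compare. The choice of cluster inputs, which is not written down, could settle that order.

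**Working it through.** **1. The plan's own figures.** Both stated sizes equal 10 × clusters × variables: 10 × 4 × 8 = 320 and 10 × 7 × 5 = 350. The factor of 10 is inferred; the plan gives no derivation. The point does not depend on these sizes. What matters is the number of variables, read here as the number of cluster inputs: 8 with 4 clusters, 5 with 7.

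**2. Is there overlap?** Physician measures enter the clustering. Only three are listed, so at least one of them, as a total or as components, is an input. The same three are then tested (SELENA-SLEDAI is taken to be the listed SLEDAI). If components rather than totals are entered, the overlap is partial. GEE handles correlation between visits of one patient and does not address this.

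**3. Could the three be treated unequally?** Entering all three leaves 8 − 3 = 5 places for patient and laboratory measures, or 5 − 3 = 2 in the 7-cluster case. With so few places, entering only one or two physician measures is plausible. The text does not settle it.

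**4. What would unequal treatment do to the ranking?** The documents give no effect sizes, so this was simulated. For measure j:

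gain(j) = C(Type 1 score, Type 2 score, measure j) − C(Type 1 score, Type 2 score),

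from logistic models of each cluster against the rest.

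Assumptions of the largest run: 350 patients, 800 visits, within-patient residual correlation 0.5. There were three patient-reported, three physician and two laboratory variables, four true classes (Type 1 high or low by Type 2 high or low) and a 4-profile model. Physician measures A, B and C separated the Type 1 groups by 1.5, 1.0 and 1.25 SD, so A is truly better than B. Two smaller runs, coded separately and also with assumed effects, repeated the comparison.

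Share of datasets in which the better measure ranked first:

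| Run | Only the weaker measure an input | All three in | All three out |
|---|---|---|---|
| 304 datasets | 1% | 92% | 71% |
| 80 datasets | 0% | 96% | 82% |
| 15 datasets per setting | 0% | 93% | 87% |

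In the 304-dataset run the true gains were 0.072 for A and 0.041 for B. With only B as an input, A scored 0.016 and B 0.075, so the order reversed. A run of the 7-cluster, 5-input option (20 datasets) gave 0%, 65% and 70%. The harm from unequal treatment is the same there, but the data are too few to separate all-in from all-out.

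**5. A check with three equally good measures.** With other assumed effects (800 independent visits), the one measure used as an input ranked first in 90%, 95% and 97% of datasets at loadings 0.4, 0.6 and 0.8. A fair share is one third. With none of the three as inputs it ranked first in 28 to 35%, and with all three in 17 to 30% (40 datasets each).

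**6. Can the bias in the gain be sized when all three are inputs?** No. With physician separation of 1.5 SD or less, mean full-input gain exceeded the true gain in every setting tried. At 2.5 SD with equal profile variances it fell slightly below (0.118 against 0.124). With free variances at 2.5 SD it was above (0.155 against 0.120). The documents fix neither the separation nor the variance form. The patient scores are tied to the clusters too, because patient measures are inputs and the SLAQ is revised from differences between clusters.

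**The case against.** The strongest reply is that this is mostly a gap in specification. The inputs are unnamed, the logistic outcome is inferred, and nothing says that only one or two physician measures will be entered. The measure is described as preliminary. No passage claims independent added value, and none says that a winning physician measure will be chosen; the SLE@Duke components in Aim 3 name the patient survey but no selected physician measure. How well a short form recovers a full-information classification is also a fair question in its own right.

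Much of this stands, and it rules out several stronger readings that a reader might infer:

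- *That the gain is inflated by a known amount.* Step 6 shows that even the sign is not fixed. Large gains for a useless measure arise when the data contain no classes, which contradicts the plan's hypothesis. Among real classes, an uninformative input gained only about 0.001 to 0.01.
- *That the plan treats the three unequally.* It leaves this open; it does not say so.
- *That improvement will be judged by comparing Hosmer-Lemeshow p-values.* The plan names that test for goodness of fit and C for discrimination, and never says this. What can be said is that the test checks calibration within one model, and that no interval is planned for the change in C.

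What the reply does not remove is the overlap, which follows from the text, or the absence of any rule that protects the comparison. An analyst could follow the plan exactly and obtain a reversed ranking.

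**Conclusion.** The point holds in a limited form, and the plan should be changed before this analysis is run. Physician measures help define the clusters, and the only three listed are then tested, on the natural reading against those clusters. A gain for any of the three that is an input is therefore not independent added value. If only some are inputs, the ranking can reverse. The direction of that result was consistent across simulations; the percentages rest on assumed effect sizes.

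No figure should be put on the bias in the gain when all three are inputs. Equal treatment makes the ranking fair, but it does not turn a full-input gain into independent evidence. Confidence is medium, because the logistic outcome and the cluster inputs have to be inferred.

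**What to change.** 1. List the inputs to the latent profile analysis. Name cluster assignment, each cluster against the rest, as the logistic outcome. Put all three physician measures in or leave all three out, and state which.
2. Judge improvement by the change in C when each measure is added to the new Type 1 and Type 2 scores, with a 95% interval from a bootstrap that resamples patients. Keep Hosmer-Lemeshow as a calibration check within each model.
3. If all three are in, describe the result as how well the patient scores recover a full-information classification. Do not read an interval that excludes zero as evidence of independent added value: it describes the precision of a gain that is partly self-prediction. As a sensitivity row, show the comparison against clusters refitted without the physician measures, and say that it understates a real gain (in the 304-dataset run, a true gain of 0.072 for A appeared as 0.007).
4. If all three are out, say that the target is a patient-and-laboratory classification.

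The cost is a few refits, a bootstrap and a more modest conclusion, with no new data. All-in uses 3 of the 8 or 5 input places. All-out gives clusters with less Type 1 information. A bootstrap that holds cluster labels fixed does not cover uncertainty in the clusters themselves, and the report should say so.
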